### Recruitment

We will achieve our target sample size through various recruitment efforts including placement of advertisements and flyers in local community recreational centers, religious centers, medical clinics and hospitals, low fee mental health clinics, and local newspapers in areas more densely populated by Asians, Hispanics and African Americans as well as through internet-based advertisements for all sites.

### Ethics and Dissemination

Clients will be under no obligation to consent, and will be informed that their decision will have no impact on their current or future treatment at UCLA. UCLA research personnel will obtain written informed consent from all participants. Changes to the protocol will be discussed by the Executive Committee and submitted as amendments to the IRB.

Individuals will be assigned a subject number upon entering the study. The post-baccalaureate research coordinator will place the participant's name and contact information on a code sheet next to their subject number. This code sheet will be stored on a password-protected computer in a locked laboratory with restricted access. Paperwork with identifying information will then be shredded. Only coded identifiers will be used for data archiving. Personal identifying information will be kept in a secure location, password-protected, and stored completely separate from any subject data that will be processed or analyzed for the research.

Results will be communicated and disseminated through publication in scientific journals, conferences, and other common research outlets. Any use of the study data would require strong contributions in the conceptualization of the paper to constitute authorship.

### Randomization and Masking

The research coordinator will enroll participants and assign them to interventions. Participants will be randomized 1:1 to either habituation or inhibition-based exposure therapy via centralized, computer-generated allocation sequences. Because of the nature of the study, only outcome assessors will be masked to group allocation.

### Statistical Methods

In order to examine the principal outcomes, we will use multilevel modeling Stata 17.0 to test a Condition x Time interaction in predicting normalized symptom scores. We will use repeated measures as a Level 1 factor and Condition as a Level 2 factor. Condition will be included as a categorical variable (Inhibitory, Habituation). For the principal analyses (LSAS and PDSS at pre-treatment, mid-treatment, post-treatment, and follow-up), Time will be included as a continuous variable. We will then follow-up with models using Time as a categorical variable involving three time-points (mid-treatment, post-treatment, 3-month follow-up) to examine differences at specific time points (post-treatment and follow-up) while simultaneously examining potential differences in the slopes of

the inhibitory retrieval and habituation condition from mid-treatment to post-treatment and post-treatment to follow-up. Similar models will be run for secondary outcomes (e.g., weekly Mini-SPIN, weekly PDSS, and BAT). Pre-treatment normalized symptom scores will be included as a covariate. As we conducted exposure therapy both in-person and remotely (due to COVID-19), we will also include Remote Therapy as a categorical factor (in-person, remote) in the models.

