### Participants

Participants will be recruited in the United States. A brief study description will be distributed via lab websites, social media, clinicaltrials.gov, and brochures to local agencies.

Inclusion criteria will consist of (1) Seeking treatment for social anxiety or panic disorder and demonstration of elevated scores (greater than two standard deviations of the normed mean) on standardized scales for anxiety (i.e., Mini SPIN or PDSS), (2) Age 18 to 65, (3) Either stabilized on psychotropic medications (1 month for benzodiazepines and beta blockers, 3 months for heterocyclics and SSRIs; self-reported) or medication-free (self-reported), (4) English-speaking, and (5) Clinical severity rating of 4 or higher on the Structured Clinical Interview for DSM-5 (SCID-5) for either panic disorder or social anxiety.

Exclusion criteria will consist of (1) Patient report of serious medical conditions – such as respiratory (e.g., chronic obstructive pulmonary disease), cardiovascular, pulmonary, neurological, muscular-skeletal diseases – or pregnancy, (2) History of suicidal ideation or self-harm in the past year; history of suicide attempts in the last 10 years, (3) History of bipolar disorder, psychosis, mental retardation or organic brain damage, (4) Substance abuse dependence within last 6 months, (5) Concurrent therapy focused on anxiety

Participants will be allowed to be in other forms of therapy, provided the therapy does not focus on anxiety (e.g., supportive counseling) and they have been stabilized on this alternative therapy for at least 6 months.

Interventions. Both interventions will entail 9 weekly exposure treatment sessions which are 60 minutes each, with the exception of first session which will be 90 minutes. Treatment sessions and laboratory assessments will be conducted at the UCLA Psychology Clinic and at UCLA's Anxiety and Depression Research Center laboratory.

Inhibitory Retrieval Condition (Experimental Comparator)

Participants will receive exposure therapy focused on maximizing extinction learning and expectancy violation. Participants will complete an OptEx Nexus to identify conditional stimuli (CS), unconditional stimuli (US), safety signals, and occasion setters. Exposures will be designed to “test out” if the US will occur. Consistent with associative learning principals, participants will conduct repeated exposure to the principal conditional stimulus (along with additional exposure to other CSs).

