## Outcome Measures

Principal and secondary outcome measures are depicted in Table 1.

**Table 1.** Self-report, behavioral, cognitive, and physiological measures at pre-treatment (week 0), weekly (sessions 1-9), mid-treatment (between week 4 and week 5), post-treatment (week 10) and at the 3-month follow up (week 24).

Week	Pre 0	Weekly (sessions 1-9)	Mid 4-5	Post 10	Follow-Up 24
Principal Outcome Measures					
S: Liebowitz Social Anxiety Scale- Self Report (LSAS-SR)	X		X	X	X
S: Panic Disorder Severity Scale-Self Report (PDSS-SR)	X	X	X	X	X
S: Clinician Severity Ratings (SCID-5)	X			X	X
Secondary Outcome Measures					
Mini-Social Phobia Inventory (Mini-SPIN)	X	X	X	X	X
Behavioral Approach Test (BAT)					
B: Duration of speech	X			X	
S: Subjective fear					
P: Heart rate					
S: Probability and Cost Questionnaire	X		X	X	X
S: Anxiety Sensitivity Index (ASI-3)	X		X	X	X
S: Positive and Negative Affect Schedule (PANAS-20)	X		X	X	X
S: Sheehan Disability Scale (SDS)	X		X	X	X
Fear Conditioning, Extinction, and Extinction Generalization Task					
C: Expectancy of unconditional stimuli	X			X	X
P: Heart rate, skin conductance					
Implicit Pavlovian Association					
C: Implicit associations for fear-relevant word stimuli	X		X	X	

B = Behavioral, C = Cognitive, P = Physiological, S = Subjective/experiential

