### **Principal Outcome Measures.**

Self-reported symptom severity of social anxiety and panic disorder at pre-treatment, mid-treatment, post-treatment, and follow-up. Self-reported symptom severity of social anxiety disorder and panic disorder will be assessed using the Liebowitz Social Anxiety Scale-Self Report (LSAS; Baker et al., 2002) and Panic Disorder Severity Scale-Self Report (PDSS-SR; Houck et al., 2002), respectively.

The LSAS is a 24-item measure of social anxiety symptoms during the past week. The measure assesses the severity (0 = none, 3 = severe) and frequency (0 = never, 3 = usually) of social anxiety and social avoidance, with total sum scores ranging from 0 to 144. Higher scores indicate greater symptom severity and frequency. The LSAS demonstrates excellent internal consistency and correlational data corroborate its convergent validity (Baker et al., 2002).

The PDSS-SR is a self-report instrument adapted from the interviewer-administered Panic Disorder Severity Scale which assesses panic disorder symptom severity. This self-report measure assesses panic-related anxiety, distress, and avoidance in the past week.

Clinician-rated severity of social anxiety or panic disorder. Clinician severity rating (0-8) of social anxiety or panic disorder will be assessed using the Structured Clinical Interview for DSM-5 (SCID-5). The SCID is a semi-structured diagnostic interview, which will be completed by trained graduate students and reliability-checked by [name] or [name]. This interview (1) diagnoses anxiety disorders, mood disorders, somatoform disorders, and substance disorders; and (2) screens for psychosis. The results of the diagnostic evaluation will be presented at weekly meetings with the [name] or [name], who will check the diagnostic judgment and eligibility of the subject. Potential participants must receive a clinical severity rating of four or higher for their social anxiety or panic disorder in order to be eligible.

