### Sample Size

We used G\*Power 3.1.9.2 with the F test family; ANOVA: Repeated measures, within-between interaction.  $p = .05$ , power = .8, two groups, two measures, correlation among measures = .5, nonsphericity correction = 1. The anticipated effect size is  $f = .165$  (equivalent to  $d = .33$ ), based on Wechsler, Kumpers, and Muhlberger (2019) meta-analysis comparing two forms of exposure therapy. Power analysis suggests we need a total N of 62 participants who complete the study. With an expected attrition of approximately 25%, our estimated enrollment sample size is  $n = 90$ .

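### The principal model has no diagnosis term although two disorders appear to be analysed together: no bias, but a small to moderate and cheaply avoidable loss of precision

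*Combined protocol and SAP*

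**What the plan says.** The Participants section admits people with a "Clinical severity rating of 4 or higher on the Structured Clinical Interview for DSM-5 (SCID-5) for either panic disorder or social anxiety". It does not exclude people who have both disorders, and no section defines a principal diagnosis.

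The Principal Outcome Measures section says "Self-reported symptom severity of social anxiety disorder and panic disorder will be assessed using the Liebowitz Social Anxiety Scale-Self Report" and the PDSS-SR, pairing the first scale with social anxiety and the second with panic. The third principal outcome is worded as an alternative: "Clinician severity rating (0-8) of social anxiety or panic disorder will be assessed". Table 1 lists both self-report scales without limiting either to one disorder.

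Statistical Methods plans a multilevel model "to test a Condition x Time interaction in predicting normalized symptom scores". It adds: "For the principal analyses (LSAS and PDSS at pre-treatment, mid-treatment, post-treatment, and follow-up), Time will be included as a continuous variable". The other terms are Condition, remote versus in-person therapy, and a baseline term: "Pre-treatment normalized symptom scores will be included as a covariate". Diagnosis does not appear. The section does not say what mean and SD the normalization uses, or whether the two scales share one model.

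The Sample Size section gives one figure for the whole trial: "Power analysis suggests we need a total N of 62 participants who complete the study".

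**The concern.** Two features suggest that the scales are meant to be combined. Normalized scores are needed only if different scales must share a unit, and one sample size is given for the whole trial. If they are combined, the participants in one model have different disorders measured on different instruments, and there is no reason to expect the same mean change in both. Whatever difference exists becomes unexplained variation in change, which is the variation against which Condition x Time is tested.

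Diagnosis is known for every participant from the eligibility interview. The model already adjusts for delivery mode, so leaving diagnosis out gives up precision that costs almost nothing to keep. At stake is some power in a trial with few completers. The validity of the comparison is not at stake.

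**Working it through.** **Inputs from the Sample Size section:** f = .165, two groups, two measures, correlation .5, alpha .05, N = 62 completers.

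**Assumptions, not in the documents:** share with social anxiety p = .5 to .8; difference between the disorders in mean change D = .3 to .8, in within-disorder SDs of change.

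**Step 1. The plan's own test.** Noncentrality is f² x N x m / (1 - r) = .165² x 62 x 2 / .5 = 6.75 on F(1, 60), so power is .725. The stated inputs therefore do not give 80% at 62: power is .7998 at 74 and .810 at 76. That is a separate point; here .725 is only the baseline for comparison.

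The same test can be written as a t test on change. The change variance is 2(1 - .5) = 1 and the arm difference in change is 4 x .165 = .66. The noncentrality is .66² x 31/2 = 6.75, as before.

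**Step 2. Omit diagnosis.** A group difference D in mean change adds p(1 - p)D² to a change variance of 1. The error variance is multiplied by v = 1 + p(1 - p)D², the noncentrality becomes 6.75/v, and the loss is equivalent to 62 - 62/v completers.

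| p | D | v | Power | Completers lost |
|---|---|---|---|---|
| .5 | .3 | 1.023 | .715 | 1.4 |
| .5 | .5 | 1.063 | .699 | 3.6 |
| .5 | .8 | 1.160 | .661 | 8.6 |
| .8 | .3 | 1.014 | .719 | 0.9 |
| .8 | .5 | 1.040 | .708 | 2.4 |
| .8 | .8 | 1.102 | .683 | 5.8 |

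For D up to .5 the largest loss is .725 - .699 = .026. The worst case in the table is .725 - .661 = .064. If the arm difference in change were .33 rather than .66, power would go from .248 to .221-.246.

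**Step 3. Cost of the extra terms.** With two more parameters the error degrees of freedom fall from 60 to 58, and power goes from .7246 to .7242.

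**Step 4. Which term does the work.** In complete-data random-intercept fits over four visits (weeks 0, 4.5, 10, 24; D = .8, p = .5; 150 data sets), adding the diagnosis main effect alone changed the Condition x Time estimate by less than 1e-15 and left its mean SE at .01022. Adding Diagnosis x Time brought the mean SE to .00999, a cut of (.01022 - .00999)/.01022 = 2.3%. A covariate that is constant within a person and has no time interaction does not touch a within-person slope contrast when data are complete.

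**Step 5. Bias.** Allocation is randomized, so diagnosis is independent of arm in expectation. In a four-visit slope simulation with no arm effect and D = .8 (6,000 runs), the rejection rate was .055 without diagnosis and .057 with it. Omission did not inflate it.

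**The case against.** The strongest reply is that a prognostic covariate is optional and that a plan without one is not wrong. That stands, and it is why this is rated as an improvement only.

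A second reply is that pooling is never stated. Statistical Methods names weekly Mini-SPIN and weekly PDSS as separate secondary outcomes for similar models, which may point to one model per scale. If each scale were analysed only in its own disorder group, a diagnosis term would be largely moot. This also stands, so the fix is conditional on the disorders being analysed together.

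A third reply is that the undefined normalization and the missing score rule are details that analysts would fill in sensibly. The text supports this in part: it refers to each participant's social anxiety or panic disorder, which implies a target disorder. An explicit rule is still missing for people with both, and one sentence would supply it.

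Four stronger readings are tempting, and the documents do not support them:

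- A reader might infer that the treatment comparison is biased. Randomization rules that out. The Randomization and Masking section names no stratification factor, but chance imbalance in diagnosis is already part of the variance in Step 2, not an addition to it.
- A reader might size the loss from a two-point analysis adjusted for baseline, which gives larger figures. That does not describe the principal test. The pre-treatment score is listed as a covariate with no time interaction, and as such it leaves Condition x Time unchanged with complete data.
- A reader might expect the baseline covariate to absorb diagnosis. For the same reason it cannot do so in this test.
- A reader might infer a severe loss of power from analysing each scale in everyone. The plan does not state that analysis, and its size would depend on effects and spreads in participants without the disorder, for which the documents give no figures.

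**Conclusion.** The concern holds as a free-to-cheap improvement. If own-disorder scores are analysed together, leaving out diagnosis raises error variance by 1-16% on the plan's own two-measure test, like losing about 1 to 9 of 62 completers. Power falls from about 72% to between 66% and 72%, and for the more modest disorder differences the loss is nearly negligible.

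The estimate rests on the pooled reading, the assumed disorder mix and difference in change, complete data, and a two-visit test standing in for the four-visit model. The absolute powers are illustrative; the relative loss is the more dependable part. Confidence is medium, mainly because pooling has to be inferred.

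**What to change.** In Statistical Methods, add principal diagnosis and Diagnosis x Time to the principal self-report and clinician-severity models wherever both disorders are analysed together. The interaction is essential, because the main effect alone recovers nothing for the principal test.

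In the same edit, state three things:

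- Each participant contributes the scale of the target disorder (LSAS-SR or PDSS-SR), and the clinician rating follows the same disorder.
- For participants with both disorders, one pre-specified rule based only on pre-treatment data fixes the target disorder.
- Scores are standardized at all visits by one fixed mean and SD per scale, from pre-treatment data or published norms. If one disorder group is small, its sample SD will be imprecise, which is a reason to consider norms.

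If the intention is instead a separate model per scale, say so and say which participants enter each; the diagnosis term is then needed only in models that contain both disorders.

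The statistical cost is one or two degrees of freedom, with no new data and no change to randomization. The administrative cost is more than a wording change. Statistical Methods already refers to therapy delivered during COVID-19 in the past tense, and Ethics and Dissemination sends protocol changes to the IRB as amendments. The edit should therefore be dated and documented as made before outcome data are examined by arm.

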### Safety Monitoring

Study staff will be available 24 hours to respond to urgent issues. All staff will be able to provide information about local emergency facilities. The therapist will generally be the first person to respond to a participant with a problem. They will handle some events immediately. If they are not able to manage the emergency event, they will contact the PIs, who will also be available 24 hours by cell phone to assist with participant management or crisis intervention.

Monitoring and reporting of all adverse events. The following adverse events will be monitored: suicide attempts, study dropout, psychiatric hospitalizations, and clinical deterioration, defined as emergent suicidal ideation or suicidal plan, or emergence of a new psychiatric or medical diagnosis or behavior posing significant risk to the subjects or others.

The following grading system will be used to assess the seriousness of any adverse events:

0 No adverse event or within normal limits

1 Mild adverse event

2 Moderate adverse event

3 Severe adverse event resulting in hospitalization or a persistent or significant disability/incapacity

4 Life-threatening or disabling adverse event

5 Fatal adverse event

Study research staff will be trained in what events to look for and to report any such events to Drs. [name]. If the event is graded 2-4, Drs. [name] will interview the Ps and take the appropriate action. Drs. [name] can be reached promptly by telephone. UCLA's IRB will be notified within 24 hours of any serious adverse events (SAEs), in the 3-5 range. Within a week of any SAEs, [name] will determine whether the adverse event affects the Risk/Benefit ratio of the study and whether modifications to the protocol (at Risks to Subjects) or consent form (at Risks and Inconveniences) are required. [name] or the IRB has the authority to stop or modify the study.

[name] will conduct a review of all non-serious adverse events at least quarterly. They will evaluate the types, frequency, and severity of the adverse events and determine if modifications to the protocol or consent form are required. If an event qualifies as a serious adverse event, then the serious adverse event will be reported to IRB. A summary of the nonserious adverse events will be reported to the IRB at minimum, when yearly re-approval of the IRB protocol is sought. The summary will include number of Ps enrolled, treatment retention and reasons for drop-out, and a synopsis of graded adverse events to date. [name] or the IRB has the authority to stop or modify the study.

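### The list of adverse events to monitor is narrower than the plan's own sub-heading, grading scale and quarterly review, so a non-psychiatric admission, a death or an exposure injury could go unrecorded.

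*Combined protocol and SAP*

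**What the plan says.** All the relevant text is in the Safety Monitoring section of the combined protocol and SAP.

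- **Scope.** The sub-heading reads "Monitoring and reporting of all adverse events".
- **List.** The next sentence says: "The following adverse events will be monitored: suicide attempts, study dropout, psychiatric hospitalizations, and clinical deterioration". It goes on to define clinical deterioration as emergent suicidal ideation or a suicidal plan, or "emergence of a new psychiatric or medical diagnosis or behavior posing significant risk to the subjects or others".
- **Grading.** The scale is introduced with "The following grading system will be used to assess the seriousness of any adverse events". Grade 3 is "Severe adverse event resulting in hospitalization or a persistent or significant disability/incapacity", and grade 5 is a fatal event.
- **Detection.** "Study research staff will be trained in what events to look for and to report any such events" to the investigators.
- **Expedited reporting.** The IRB "will be notified within 24 hours of any serious adverse events (SAEs), in the 3-5 range".
- **Routine review.** The end of the section provides for a review, at least every quarter, of all events that are not serious. It also repeats that any event qualifying as serious goes to the IRB.

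The section gives no general definition of an adverse event.

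**The concern.** The section works as a chain: staff notice an event, report it to the investigators, it is graded, and a grade of 3 or higher starts the 24-hour clock for the IRB. Every step after the first depends on the event having been noticed and recorded. The only guidance on what to notice is the list, and the list is narrower than the scale that follows it. The scale expects hospitalizations of any kind and deaths; the list names psychiatric hospitalizations and no deaths.

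At stake is the completeness of the safety record. The events most exposed to the gap are physical ones, including injury during an exposure exercise, which is a harm that the interventions themselves could cause. In the habituation arm, in-session exposures are repeated between sessions, and the amendment log moves therapy sessions to video from March 2020. Staff will therefore not witness every event and depend on knowing what to ask about.

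**Working it through.** No arithmetic applies. The check compares the list with the other statements of scope in the same section, then takes types of event one at a time.

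**Scope, side by side**

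| Element of Safety Monitoring | Scope as written |
|---|---|
| Sub-heading | All adverse events |
| Monitored list | Four items; the fourth includes a new psychiatric or medical diagnosis, or behavior, posing significant risk |
| Grading scale | Any adverse event |
| Grade 3 | Hospitalization with no psychiatric qualifier, or disability/incapacity |
| Grade 5 | Any fatal event |
| 24-hour IRB notice | Any serious event, grades 3 to 5 |
| Quarterly review | All non-serious events |

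Six of the seven elements carry no psychiatric restriction and are not tied to named items. The list is the exception.

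**Coverage by type of event**

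1. *Psychiatric admission.* Listed by name.
2. *Admission for a new medical diagnosis posing significant risk.* Listed, through clinical deterioration.
3. *Admission for worsening of a pre-existing medical condition.* Not clearly listed, since the diagnosis is not new. Grade 3 if recognised as an adverse event.
4. *Death.* Not named. A death by suicide would reasonably be picked up under suicide attempts, and a death from a newly diagnosed risky condition under clinical deterioration. A death from another cause, such as an accident, falls under no item. Grade 5 if recognised as an adverse event.
5. *Injury during an exposure.* Not named. It is listed only if someone classes it as a new medical diagnosis posing significant risk.
6. *Mild physical event.* Not listed, although grades 1 and 2 and the quarterly review presuppose that such events are collected.

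**Where the chain can break.** For types 3 to 5 the grading and reporting rules are adequate once the event is known. The weak step is detection: staff are trained on which events to look for, and the section specifies no events beyond the list. Two therapists who read it in good faith could record different things.

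**The case against.** The strongest reply is that the surrounding text is broad and would govern in practice. The sub-heading, the grading scale and the IRB rule all speak of all or any events, and IRB notice depends on grade and not on membership of the list. The clinical-deterioration clause already brings in new medical diagnoses that pose significant risk. The therapist is generally the first responder to a participant with a problem of any kind, and sessions are weekly. People who report serious medical conditions or pregnancy are excluded at entry, which reduces the number who could be admitted for a pre-existing condition.

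Much of this stands, and it rules out three stronger readings.

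- A reader might infer that medical events are left out of serious-event reporting. They are not: the clause on new diagnoses covers many of them, and any recognised event graded 3 to 5 goes to the IRB.
- A reader might infer that the list is exhaustive and that an unlisted event can never be graded. The section does not say so. It also does not say that staff training is confined to the list.
- A reader might infer that counting dropout as an adverse event swamps the safety data. The documents do not support this. Monitoring dropout is a defensible choice, the yearly IRB summary names retention and reasons for drop-out separately from graded events, and no pooled adverse-event total is planned.

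The reply does not remove the mismatch itself. The exclusion rests on patient report and concerns serious conditions only, and it does nothing about injury or accidental death. Broad reporting rules do not help with an event that nobody was told to ask about.

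**Conclusion.** The point holds as a gap in ascertainment. Apart from its clause on new risky diagnoses, the monitored list is narrower than the sub-heading, grades 3 and 5, and the quarterly review. A non-psychiatric admission, a death outside the listed items, or an exposure injury not seen as a new risky diagnosis could go unrecorded and so might not reach grading.

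The size cannot be stated, because the documents give no expected rate for any of these events. No endpoint, sample size or planned analysis is affected. The conclusion rests on one assumption: that staff take the list as their working guide to what to record. That is the natural reading, since the section specifies no other events to look for, but it remains a reading. The correction is worth making because it is cheap and concerns the completeness of safety capture.

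**What to change.** Reconcile the list with the sub-heading and the grading scale:

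1. Replace psychiatric hospitalizations with hospitalization for any cause.
2. Add death from any cause.
3. Add injury during an assigned exposure, in session or between sessions.

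Keep the other items as they are, including clinical deterioration and its definition. Use the same wording in the staff training and on the event form, so that what staff look for matches what the scale grades.

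The cost is a short change of wording in Safety Monitoring and a few more form entries. Only the recording of events changes; participant care, the outcome measures and the analysis do not.
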